Effect of number of remote limb ischemic conditioning cycles of learning enhancement.

NCT03512041

NIHR01HD085930-Aim2

05/19/2017

Effect of number of remote limb ischemic conditioning cycles of learning enhancement.

Study Objectives	
The objective of this research study is to determine if remote limb ischemic conditioning (RLIC) can serve as an agent to enhance motor and cognitive learning. The immediate goal is to test the effect of number of RLIC cycles on motor learning in neurologically intact adults. An additional goal is to determine a physiological marker of the effectiveness of RLIC through collecting blood samples during various time points throughout the study. The long term goal is to determine if RLIC, when compared to sham treatment, augments the learning that occurs during a rehabilitation training exercise in people who have motor deficits following stroke.

Background Rationale	
It is now understood that the nervous system has remarkable adaptive capacity. Specifically, the central nervous system retains its ability to reorganize in structure and function in response to behavioral experience in neurologically intact people and in individuals with neurological injury. Cognitive and motor learning guide the adaptation of the central nervous system and are essential components of effective training paradigms.
 
There is a growing body of literature which suggests that inducing a transient state of systemic ischemia has the potential to induce spinal plasticity, strengthen spared pathways to motoneurons, and lead to improved motor recovery following neurological injury.^{1,2} Specifically, daily systemic ischemic conditioning has been shown to improve both forelimb and respiratory motor function in rodent models of chronic cervical spinal injury.^{1,3} Moreover, systemic ischemic conditioning resulted in increased ankle strength (single session)² and augmented walking speed and endurance (5 sessions)⁴ in humans with motor incomplete spinal cord injuries.
 
In a related area of research, it has been shown that ischemic conditioning administered peripherally represents a strategy for harnessing the body's endogenous protective capabilities against lethal levels of ischemia. With this technique, applying brief ischemia and reperfusion to a remote organ or tissue results in significantly reduced damage from subsequent exposures to ischemia. For example, applying a tourniquet and creating hypoxia in a rat's hindlimb for 10 minutes reduced the extent of cardiac abnormalities following a sustained ischemic insult.⁵ This same phenomenon has been shown in humans. Applying an inflated blood pressure cuff to the upper or lower limb has shown efficacy for protection in people undergoing cardiac surgeries,^{6,7} undergoing elective surgery to repair abdominal aortic aneurysm,⁸ experiencing MI,⁹ and with symptomatic intracranial arterial stenosis.⁷
 
The mechanisms underlying the neuroplastic and neuroprotective effects of ischemic conditioning are not fully understood. At this time, the literature indicates that there are both humoral and neural mechanisms responsible for the protection and the plasticity. It is clear that ischemic conditioning results in widespread physiological effects and that the observed effects work through multiple mechanistic pathways.
 
The next translational step is to investigate whether combining ischemic conditioning with behavioral training has the ability to augment motor learning. Specifically, we will employ remote limb ischemic conditioning (via inflation/deflation of a blood pressure cuff) with the objective of activating the endogenous pathways shown to elicit neuroplasticity. If eventually effective, RLIC could have profound effect on the rehabilitation and recovery of motor


	
function in people with stroke. It is important to first start this translational investigation in neurologically intact people in order to determine optimal protocols for people with stroke.
 
The purpose of this study is to test the effect of number of RLIC cycles on motor learning in neurologically intact adults and if we can find a physiological blood marker related to effective administration of RLIC. We hypothesize that 3 cycles of RLIC will be sufficient to enhance motor learning compared to sham conditioning, and that there will be a dose-dependent (number of cycles) response in learning, thus making training more efficient, more effective, and longer-lasting. Determining the number of cycles necessary to elicit the benefits of RLIC is important in developing the most effective and least burdensome treatment for future patients with motor deficits.
																
Study Design	
Between subjects repeated measures design. Please refer to Figure 1.
																
Groups	
Group 1: Neurologically Intact Subjects + 5 cycles of RLIC Group 2: Neurologically Intact Subjects + 4 cycles of RLIC Group 3: Neurologically Intact Subjects + 3 cycles of RLIC Group 4: Neurologically Intact Subjects + 5 cycles of sham conditioning
 
Subjects who qualify and consent will be randomly assigned to either group 1, 2, 3 or 4. Allocation will be concealed from those responsible for assessing patients for eligibility and entry into the study.
																
Number of Subjects & Power Analysis	
Based off of pilot data on the balance training task, we need the following total sample sizes moving forward (see Table 1 below) to achieve at least 80% power to detect the mean differences of change scores (posttest – pretest) between the two treatment groups (RLIC vs. sham) based on a two-sample t-test at a significance level of 0.05. The standard deviations for change scores are assumed to be 2.5 seconds and 1.9 seconds for the RLIC and sham groups, respectively. 10 subjects will be enrolled for each of the 4 groups. However, we request permission to enroll 55 subjects total to allow for screen failures and participants who do not complete all study visits. This will give us the ability to detect differences on the balance task of at least 3-4 seconds. Differences less than this (and smaller effect sizes) are unlikely to be clinically-relevant in future target populations.
 
Table 1. Power analysis
 
  
 Mean difference of change score	Total sample size (assume equal sample size in each group)	
   
 7 seconds	12 (with actual power 93%)	
 
 6	12 (with actual power 85%)	
 
 5	15	
 
 4	21	
 
 3	30	
 
 2	63	
 
 1	237 study visits.	
  
	Mean difference of change score	Total sample size (assume equal sample size in each group)	7 seconds	12 (with actual power 93%)	6	12 (with actual power 85%)	5	15	4	21	3	30	2	63	1	237 study visits.
Mean difference of change score	Total sample size (assume equal sample size in each group)																
7 seconds	12 (with actual power 93%)																
6	12 (with actual power 85%)																
5	15																
4	21																
3	30																
2	63																
1	237 study visits.																
Inclusion & Exclusion Criteria	
Inclusion Criteria: ¶ 1)Between the age of 18 and 40 years ¶ ¶ Exclusion Criteria: ¶ 1)History of neurological condition (i.e. stroke, Alzheimer's disease, Parkinson's disease), ADD, ADHD, balance impairment, or vestibular disorder ¶ 2)History of sleep apnea ¶ 3)History of lower extremity condition, injury, or surgery which could compromise performance on motor training task ¶
																

	
4)Any extremity soft tissue, orthopedic, or vascular injury (i.e. peripheral vascular disease) which may contraindicate RLIC ¶
 
5)Any cognitive, sensory, or communication problem that would prevent completion of the study ¶
 
6)Current intensive weight lifting or interval training exercise ¶
 
7)Current substance abuse or dependence ¶
 
8)Current use of medication with selective serotoninreuptake inhibitors.
 
9)Unwillingness to travel for all study visits ¶

Concomitant Medications/Training
	
Medications for the management for other co-morbid conditions not listed in the exclusion criteria are permitted. Regular, light exercise is permitted. See exclusion criteria for exercise that is not permitted.


Order of Experiment/ Study Visits
	
This study involves 8 total visits. Participants will be in the study for up to 6 weeks. Please refer to Figure 1 for details about study visits.
 
D1: Subjects will be asked to avoid food, drink (except water), and vigorous exercise beginning midnight the day of their visit. A trained clinical interviewer will provide informed consent and conduct a structured clinical interview. Eligible individuals will be asked to complete descriptive measures. Next, subjects will have an electrocardiogram (ECG) recording while they sit quietly for 7 minutes. Then, subjects will undergo a blood draw (4 teaspoons). Next, researchers will gather baseline measurements on all primary and secondary outcome measures. Subjects will then be randomized to their treatment group. After randomization, subjects will undergo their assigned dose of RLIC or sham conditioning. After conditioning, subjects will have another 7-minute resting ECG recording and undergo another blood draw (4 teaspoons). This visit will take approximately: 2.5 hours
 
D2: Subjects will be asked to avoid food, drink (except water), and vigorous exercise beginning midnight the day of their visit. Subjects will undergo a blood draw (4 teaspoons). Then, subjects will undergo their specified dose of RLIC or sham conditioning. This visit will take approximately: 1 hour
 
D3-6: Subjects will undergo their specified dose of RLIC or sham conditioning. Next, behavioral training will commence (a balance task, arm task, and computer task). The order of behavioral training task practice will be randomized. These visits will take approximately: 2 hours
 
D7: Subjects will be asked to avoid food, drink (except water), and vigorous exercise beginning midnight the day of their visit. Subjects will undergo a blood draw (4 teaspoons). Then, subjects will undergo their specified dose of RLIC or sham conditioning. Next, subjects will complete behavioral training tasks and post-testing. This visit will take approximately: 2.5 hours
 
F/U: Post-test performance assessment on the primary and secondary outcome measures will be performed. Participants will not receive RLIC or sham conditioning during the follow-up visits. Participants will fill out a survey indicating whether they think that they received RLIC or sham treatment. This visit will take approximately: 45 minutes


RLIC Treatment Parameters
	
Remote limb ischemic conditioning will be achieved via blood pressure cuff inflation to 20 mmHg above systolic blood pressure on the non-dominant, upper extremity regardless of the assigned number of cycles. Sham conditioning will be achieved via blood pressure cuff inflation to 10 mmHg under diastolic blood pressure on the non-dominant, upper extremity.

	Subjects will be blinded to their group assignment (RLIC or sham conditioning).
Behavioral Training Parameters	
Three tasks will be used for behavioral training on D1-D7.
 
 1) Balance training task (15 minutes; rest breaks as needed) 2) Arm training task (10 minutes; rest breaks as needed) 3) Computer training task (10-20 minutes) 
The balance task requires subjects to stand on a movable platform (stability platform, model 16030L, Lafayette Instrument) and to keep the platform in a balanced, horizontal position.¹⁰ This is a lab-based test. This task was selected because it simulates the balance required for daily function, and can be easily modified to the appropriate level of difficulty in accordance with each subject's motor abilities.
 
The arm task is a cup stacking task. Subjects are asked to stack ten cups in three different arrangements, using bilateral upper extremities. This task should be completed as quickly as possible.
 
The computer training task is a discrete sequence production task. The computer task involves having subjects learn six, 10-element sequences of key presses. Each sequence is uniquely cued before commencement. 5 boxes are shown on the screen and subjects respond by pressing a key on the keyboard with their right hand that corresponds to the position of the boxes on the screen. This particular task was selected because it can improve with practice.¹¹

Descriptive measures	Demographic information, including age, dominant side, gender, ethnicity, race, level of physical activity, height, body weight, employment status, education level, co-morbidities, and current medications will be collected on all subjects on D1.
Primary Outcome Measures	
The primary outcome measures are:
 
 1) Performance on the standing balance motor task 2) Performance on the arm task 3) Performance on the computer task 
Performance on the standing balance task will be quantified by the identifying the number of seconds in a 30-second trial that an individual is able to maintain the platform within $\pm 3^\circ$ of horizontal. Performance on the arm task will be measured by the time to complete the three cup-stacking structures. The measure of performance on the computer task will be the average time to complete each unique sequence in milliseconds.
 
Please refer to Table 1 for a summary of the assessment schedule.

Secondary Outcome Measure	
The secondary outcome measure is:
 
 1) Blood draw: probe for levels of serum markers of RLIC 
The blood draw will be performed by trained members of the Washington University Clinical Research Unit. Blood will be processed the Washington University CORE Laboratory. Please refer to Table 1 for a summary of the assessment schedule.

Data Analysis	Data will be analyzed using a mixed model ANOVA with a within subject factor of time (pretest vs. posttest) and a between subjects factor of conditioning (RLIC vs. sham treatment).
Safety Considerations & Monitoring	The study will be submitted to and approved by the Washington University Human Research Protection Office prior to initiation. The risks of participating in the rehabilitation

	
intervention are minimal and are similar to the risks encountered during routine physical and occupational therapy services. The most likely risk during training tasks is fatigue. Subjects will be encouraged to take rest breaks as needed. There is also a small risk of falling during participation in the balance task portion of this study. Subjects will be permitted to use a handrail as needed for safety during lower extremity balance tasks and performance of all tasks will be supervised by a study team member.
 
With regards to the RLIC, rare side effects may occur, including HTN, hippocampal cell death, learning deficits, and metabolic syndrome. However, this protocol involves between 3 and 5 cycles of peripheral ischemia, which is below the dose that has been found to be harmful. This number of RLIC cycles is associated with tolerable pain and does not cause changes in systematic blood pressure or heart rate, and has not resulted in side effects.⁹
 
In order to monitor for safety, we will continuously monitor for headaches, pain, lightheadedness, dizziness, altered vision, respiratory distress, cyanosis, and spasms. We will record and monitor heart rate, blood pressure, and oxygen saturation before, during, and after each session of RLIC. Sessions will be terminated if heart rate <40 bpm or >160bpm, systolic BP <85mm Hg or >160mmHg, or if O₂ saturation <75%. Moreover, during the follow up session, all subjects will be asked to fill out a questionnaire related to the presence of adverse effects that resulted from participation in this study.

Investigators	PI: [name] [name] Co-I: [name], MD, PhD Study Coordinator: [name]
Number of Centers	1 center: Washington University School of Medicine
Key References	Please see the reference list.

[figure not shown]

Figure 1. Remote limb ischemic conditioning (RLIC) involves between 3 and 5 cycles (depending on the group randomization) of 5 minutes of upper extremity peripheral ischemia (induced either by a blood pressure cuff inflated to 20 mmHg >systolic BP), alternating with 5 minutes of no ischemia. For 5 consecutive weekdays, subjects receive a combinational intervention of RLIC (or sham) plus training. On training days, subjects undergo the RLIC and perform 15 minutes of balance training, 10 minutes of arm training, and 20 minutes of computer training.

Table 1

Assessments	Time Points							
	Day 1	Day 2	Day 3	Day 4	Day 5	Day 6	Day 7	Follow-up
Fast Prior to Visit	X	X					X	

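### Three unranked primary tasks have no rule for success or for sharing error; a fixed testing order starting with the balance task would close the gap.

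*Combined protocol and SAP*

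**What the plan says.** Primary Outcome Measures begins "The primary outcome measures are" and names three tasks on an equal footing: "1) Performance on the standing balance motor task 2) Performance on the arm task 3) Performance on the computer task". The Data Analysis row is one sentence. It gives a mixed model ANOVA with time at two levels and "a between subjects factor of conditioning (RLIC vs. sham treatment"), with no mention of multiplicity.

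A significance level appears only in Number of Subjects & Power Analysis, where the sizing is "based on a two-sample t-test at a significance level of 0.05". That calculation is "Based off of pilot data on the balance training task", and its SDs are for that task alone: "The standard deviations for change scores are assumed to be 2.5 seconds and 1.9 seconds for the RLIC and sham groups, respectively". The section gives no SD, target difference or power for the arm or computer task. On numbers, "10 subjects will be enrolled for each of the 4 groups", three of them RLIC and one sham.

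Study Objectives asks whether RLIC "can serve as an agent to enhance motor and cognitive learning". The hypothesis in Background Rationale concerns motor learning in general and names no deciding task.

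**The concern.** The written analysis implies three RLIC-versus-sham tests, one per task. At least four success rules fit the text: any one task, all three, balance as the lead, or three separate claims. They have different error rates, and the plan does not choose among them.

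The objective is worded broadly enough that one positive task could be presented as support for it. If that happened without adjustment, the overall false-positive chance would usually exceed the level of a single test. Background Rationale says the work is meant to settle protocols for later use in people with stroke, so a false lead could carry forward.

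**Working it through.** **Inputs from the document.** Four groups of 10, so the two-level factor compares 30 RLIC with 10 sham. Balance change-score SDs are 2.5 s (RLIC) and 1.9 s (sham). The level is 0.05 and target power is at least 80%.

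**Assumed, because not in the document.** Two-sided tests; 0.05 for each task in the analysis; arm and computer SDs; a common correlation between tasks of 0, 0.5 or 0.8.

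**1. The plan's own figure.** For 10 v 10 and a 3 s difference, SE = √(2.5²/10 + 1.9²/10) = 0.993. The noncentrality is 3/0.993 = 3.02, with 18 df and critical value 2.101. Power is 81.5%, so the stated 80% at 10 per group reproduces.

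**2. Form of the test.** With two time points, the time-by-conditioning test is the equal-variance t-test on change scores. I take this as the test of learning.

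**3. Simplest case.** Three independent tests that each hold 0.05 give 1 − 0.95³ = 14.3%.

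**4. Effect of the stated SDs on one test.** The true variance of the 30 v 10 difference is 2.5²/30 + 1.9²/10 = 0.569. The equal-variance formula expects [(29 × 6.25 + 9 × 3.61)/38] × (1/30 + 1/10) = 5.625 × 0.1333 = 0.750. The test statistic is therefore too small by a factor √(0.569/0.750) = 0.871. The effective cut-off is 2.024/0.871 = 2.32 on 38 df, which is about 2.6% and not 5%. The test is conservative because the larger group has the larger SD.

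**5. Chance of at least one false positive in three tasks.** Simulation under the null, 30 v 10, 200,000 replicates for each case in the first three rows:

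| SDs (RLIC v sham), equal-variance test | r = 0 | r = 0.5 | r = 0.8 |
|---|---|---|---|
| Equal on all tasks | 14.3% | 12.5% | 9.9% |
| 2.5 v 1.9 on balance only, equal on the others | 12.1% | 10.9% | 8.7% |
| 2.5 v 1.9 on all tasks | 7.5% | 6.8% | 5.4% |
| 2.5 v 1.9 on balance, 1.9 v 2.5 on the others | 18.6% | 16.8% | 13.7% |

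A Welch test gives about 14.5 / 13 / 10% for the first three SD patterns, so removing the equal-variance assumption alone does not deal with multiplicity. At r = 0.9 with 2.5 v 1.9 on all tasks, the equal-variance figure falls to 4.6%.

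**6. Error in favour of RLIC only (nominal 2.5%).** At r = 0 / 0.5 / 0.8: 7.3 / 6.2 / 4.9% with equal SDs, 6.2 / 5.5 / 4.3% with balance only unequal, and 3.8 / 3.3 / 2.7% with all unequal. In the reversed case it is, by symmetry, at least half the two-sided figure: 18.6/2 = 9.3% at r = 0.

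**7. If all three tasks had to succeed.** With the first three SD patterns, the error is at most 1.3% up to r = 0.8, so there is no inflation.

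**8. Balance power at 3 s under two remedies.** A balance-first order tests balance at the full 0.05, so its power is unchanged. Holm starts at 0.05/3:

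| Comparison | At 0.05 | At 0.05/3 |
|---|---|---|
| 30 v 10, SE = 2.372 × √(1/30 + 1/10) = 0.866 | 92.2% | 82.6% |
| 10 v 10, SE = 0.993 | 81.5% | 65.0% |

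**The case against.** - **Balance is already the lead task.** It is listed first and is the only task sized. That is a reasonable guess at intent, but the document does not rank it. If it is the intent, writing it down costs nothing.
- **Adjustment is not always needed.** This stands. Requiring all three tasks gives no inflation, and if each task is its own question, family-wise control is optional. The plan states neither.
- **The figures depend on assumptions.** This stands. A reader might infer that the plan has a 14% false-positive rate, or that 5-14% is the possible range. The document supports neither: arm and computer SDs, correlations and sidedness are absent, and the table has values on both sides of that range.
- **The harm is directional.** This also stands. A false claim of benefit is the smaller figure, about 3-7% in the cases with RLIC at least as variable as sham.
- **Adjustment weakens the study.** This is true of Holm for a single cycle group against sham. The claim that Holm stays above 80% holds only for the 30 v 10 contrast.
- **Other choices also multiply tests.** The comparisons between cycle numbers, and Day 7 against follow-up as the post-test, are further sources. A rule for the three tasks does not cover them.

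A reader might also infer that sizing on balance alone is an error. It is not: using the task with pilot data is acceptable.

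**Conclusion.** The gap is real: three equal primary tasks, one analysis sentence, and no success or multiplicity rule. That any single positive task would be called success is a conditional reading, since the document is silent.

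Under that reading, with three two-sided 0.05 tests on 30 v 10, the false-positive chance is about 10-14% with equal SDs and about 5-8% with the balance SDs on every task. Both ranges are for correlations of 0 to 0.8. The lower range reflects a conservatism that would disappear with equal SDs or a Welch test, and would turn to inflation on any task where sham is the more variable group.

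The plan should be changed, but the consequence is modest in a single-centre study of 40 healthy adults.

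**What to change.** Keep all three tasks as primary and add to the Data Analysis row:

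- The tasks are tested in a fixed, named order starting with balance. Each next task is tested at two-sided 0.05 only if the one before is significant.
- The 0.05 level applies to the analysis as well as the sizing.
- The test does not assume equal variances, for example a Welch t-test on change scores.
- The rule covers the three tasks only. The cycle-number comparisons and the choice of post-test visit need their own statements.

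This is wording only, with no extra subjects and no loss of balance power from the ordering. The price is that the arm and computer tasks cannot be claimed as confirmatory if balance fails.

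Holm is an alternative for the 30 v 10 contrast only. For a 10 v 10 comparison of one cycle group with sham, it would take 3 s power below the stated 80%. If three separate claims are intended, the plan should say so, and add that no overall claim will rest on one task.

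### Optional improvement, not an error: the planned pre/post ANOVA is a valid change-score test, but using the Day 1 score as a covariate costs no data and may raise power for a single dose arm against sham

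*Combined protocol and SAP*

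**What the plan says.** The Data Analysis section is one sentence. It says "Data will be analyzed using a mixed model ANOVA with a within subject factor of time (pretest vs. posttest" and then adds "a between subjects factor of conditioning (RLIC vs. sham treatment". It names no covariate, does not say which model term is the test, and does not say which visit supplies the posttest. Order of Experiment/Study Visits places post-testing on Day 7 and again at follow-up.

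The section on number of subjects and power sizes the study "to detect the mean differences of change scores" by a two-sample t-test at the 0.05 level. It states: "The standard deviations for change scores are assumed to be 2.5 seconds and 1.9 seconds for the RLIC and sham groups, respectively". On enrolment it says "10 subjects will be enrolled for each of the 4 groups", and on sensitivity "This will give us the ability to detect differences on the balance task of at least 3-4 seconds".

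On Day 1, before randomization and before any conditioning, "researchers will gather baseline measurements on all primary and secondary outcome measures". The Background Rationale hypothesizes that 3 cycles improve learning relative to sham. That contrast has 10 participants on each side.

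**The concern.** A change score subtracts the whole pretest, which amounts to assuming that the posttest rises by one unit for each unit of pretest. If the true slope differs from 1, part of the baseline noise stays in the comparison. An ANCOVA estimates the slope and removes that part. Because the Day 1 score precedes randomization, it is a legitimate covariate, and it is already collected.

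What is at stake is precision only. The contrast with least margin is a single dose arm against sham at 3 s, the lower end of the stated 3-4 s range, where power is close to the 80% target.

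**Working it through.** **Inputs from the documents.** Change SDs 2.5 s (RLIC) and 1.9 s (sham); 10 per group; four groups; alpha 0.05, taken as two-sided because that reproduces the plan's table; target difference 3-4 s.

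**Assumptions, because the documents give neither.** rho is the pre/post correlation, and k is the posttest SD divided by the pretest SD. All 40 participants are assumed to be analysed.

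**1. The plan's own figure.** A two-sample t-test with unequal variances (Satterthwaite) needs 4, 4, 5, 7, 10, 21 and 79 per group for differences of 7 s down to 1 s. Multiplied by three, these are the power table's 12, 12, 15, 21, 30, 63 and 237. Simulated power at 4 per group is 93.1% (7 s) and 84.5% (6 s), against the stated 93% and 85%. The 3 s row therefore corresponds to 10 per group, the size used below.

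**2. Equivalence.** In a numerical example with two time points, the mixed-ANOVA group-by-time F and the squared t on change scores were both 5.699.

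**3. Change score, 10 vs 10.** Pooled SD = sqrt((2.5² + 1.9²)/2) = 2.22. Standard error = 2.22 × sqrt(2/10) = 0.993. At 3 s the noncentrality is 3/0.993 = 3.02 on 18 df, giving power of 81.5%. At 4 s power is 96.8%.

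**4. ANCOVA, 10 vs 10.** In units of the pretest variance, the change variance is 1 + k² − 2·rho·k and the ANCOVA residual variance is k²(1 − rho²). Their ratio is

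k²(1 − rho²) / (1 + k² − 2·rho·k),

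which is (1 + rho)/2 at k = 1 and equals 1 when rho·k = 1. The contrast variance is the residual variance × (2/10) × (1 + F/18), with F distributed as F(1,18) to allow for chance baseline imbalance. Power is noncentral t on 17 df, averaged over F. Power (%) at 3 s, against 81.5% for the change score:

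| k | rho 0.3 | 0.5 | 0.7 | 0.8 | 0.9 | 0.95 |
|---|---|---|---|---|---|---|
| 0.8 | 97.2 | 95.4 | 93.6 | 93.1 | 94.2 | 96.8 |
| 1 | 92.8 | 89.0 | 85.0 | 83.0 | 81.0 | 80.0 |
| 1.25 | 87.6 | 83.3 | 79.7 | 79.0 | 81.0 | 86.5 |
| 1.5 | 84.1 | 80.4 | 79.0 | 80.8 | 87.9 | 96.0 |

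Break-even is a variance ratio of about 0.94. The worst case, a ratio of 1, gives 79.0%, a loss of 81.5 − 79.0 = 2.5 points. At 4 s, the lowest ANCOVA power found was 95.6%, against 96.8%.

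**5. Four-arm model, one dose arm vs sham, 3 s (simulated, SD 2.5 in three arms and 1.9 in sham).** The change score gives 80.2%. For rho 0.3, 0.5 and 0.7, ANCOVA gives 92.2%, 88.7% and 84.7% at k = 1, and 87.2%, 83.1% and 79.7% at k = 1.25. The lowest value is 78.9% (k = 1.25, rho 0.8), a loss of about 1.3 points.

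**6. Pooled RLIC vs sham as written, 30 vs 10, 3 s.** By formula, SD = sqrt((29 × 2.5² + 9 × 1.9²)/38) = 2.37 on 38 df, giving 92.2%. Simulated with the separate SDs, the change score gives 94.6%. Simulated ANCOVA gives 94.4% to 99.3% at k = 1 and 94.0% to 97.8% at k = 1.25.

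**7. Type I error (simulated, k = 1, 1.25 and 1.5).** ANCOVA gives 4.9% to 5.3% at 10 vs 10, 3.2% to 3.9% in the four-arm model and 1.4% to 2.6% at 30 vs 10. The change score gives 5.0% to 5.3%, 3.6% to 4.0% and 2.5% to 2.6%. The adjustment causes no inflation.

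**The case against.** The planned test is valid, matches its power calculation and meets the 80% target at 3 s even for 10 vs 10. For the comparison that the Data Analysis section actually names, RLIC against sham, power is already high. The 10 vs 10 contrast comes from the hypothesis, not from the analysis sentence. The gain also depends on two unreported quantities. At k = 1 it is 3.5 to 11.3 points over rho 0.7 to 0.3, but the corresponding range is −1.8 to +6.1 at k = 1.25 and −2.5 to +2.6 at k = 1.5.

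All of this stands, and it limits the point to an optional improvement. What remains is that the covariate is free and the loss is bounded at about 2.5 points, while the possible gain is several times larger.

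A reader might infer that the plan ignores baseline, that its analysis is wrong, or that the trial is underpowered for its stated target. The documents support none of these: the change score uses the Day 1 value, and power at 3 s exceeds 80%. Nor do they show that ANCOVA would certainly gain power in this trial.

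**Conclusion.** The point holds as a cheap improvement at the lowest, optional level of severity. The mixed ANOVA may stand as written without harm to validity.

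For one dose arm against sham at 3 s, replacing the fixed slope with an estimated one moves balance-task power from 81.5% to between 79.0% and 97.2% over the assumed values examined. The direction depends on rho and k. For pooled RLIC against sham, and at 4 s, the choice matters little.

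These figures rest on the plan's change SDs, 10 analysed per group, a common slope across arms and reading the group-by-time term as the test. That reading is an inference from the change-score basis of the power section. No size of gain is claimed for the arm and computer tasks, because the documents give no SDs for them.

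**What to change.** In the Data Analysis section, state that the primary analysis of each task's Day 7 posttest is an ANCOVA with that task's Day 1 score as covariate and conditioning (RLIC vs sham) as the factor, unchanged from the present text. Use the same covariate in any single-dose against sham contrast made for the 3-cycle hypothesis. Keep the change-score mixed ANOVA as a sensitivity analysis. Fix all of this before outcome data are examined.

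The power section opens with "Based off of pilot data on the balance training task". If those data yield rho and the two SDs, report them, so that the ratio in step 4 of the working shows what to expect for the balance task. The pilot's size is not stated, so the result should be read as a guide only.

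The cost is a change of wording, with no extra participants or measurements. The statistical price is one degree of freedom and estimation of the slope: at most about 2.5 points of power at 3 s for 10 vs 10, or about 1.3 points in the four-arm model, when rho·k is near 1. The figures above already include it.
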